1. CLINICAL PROTOCOL

1.1 Background

- 5-Fluorouracil (5-FU) is an antimetabolite that works by irreversibly inhibiting the enzyme thymidylate synthetase resulting in impaired DNA synthesis. This reduces fibroblast proliferation, and inhibits collagen type 1 production which is a key protein in scar formation. This medication is commonly used in ophthalmology after or during glaucoma filtration surgery. We propose a randomized controlled prospective study to evaluate the outcome of periocular full thickness skin grafts with or without the use of 5-FU injected in the post-operative period.
- In oculofacial surgery, full thickness skin grafts are a fundamental tool used to restore function to the eyelid. This can be required after removal of skin cancer, correction of eyelid malposition such as cicatricial eyelid ectropion, retraction, scar formation, or trauma with loss of tissue. These conditions affect patients of all ages, ranging from newborns to nonagenarians. Skin grafting in the periorbital area is relatively safe, although complications may arise. The most common and challenging complication is scarring and graft shrinkage. This can lead to requiring additional surgery to add additional skin or to improve the appearance of the graft. In addition to the morbidity of another surgery, some patients have limited or no additional skin available (e.g. young patients, burn patients). The eyelid skin is the thinnest of the body, so only thin skin can be used as donor material. However, the amount of skin available for this purpose is very little. There are limited options for preventing graft shrinkage and scarring in this situation. The oldest and most commonly used technique is injection of steroid medication. Steroids decrease

proliferation of a fibroblast cells, which create collagen and glycosaminoglycan, two proteins created by the body that contract and cause graft shrinkage. Data in literature shows that one form of steroid, triamcinolone, is effective for this purpose. However, there is a risk of embolization of this solid steroid material that can rarely cause blindness. In addition, in the periocular area, steroids can elevate intraocular pressure causing glaucoma in some cases and accelerate the formation of cataracts.

1.2 Rationale

- There have been two retrospective studies that have investigated the safety and efficacy of 5-FU injected in periorbital skin grafts with or without Kenalog. The first (Massry 2011) used post-operative injections of a 50:50 mixture of 5-FU and triamcinolone for correction of medial canthal webs. In 2 patients, they found it to be safe and effective. The author noted he has used it previously for other scar management cases and was “very pleased with the results and [had] negligible side-effect[s].” The same author performed another study using 5-FU for skin grafts. This study evaluated 19 patients who had skin grafts for various purposes and were injected following surgery (similar to our protocol). This study demonstrated safety of the injection, with no cases of complication. The author concluded that the 5-FU is effective with “minimal scarring, high patient and surgeon satisfaction, and few complications
- Medication will be injected in the periocular skin graft area 2-3 weeks after surgery. The medication will be injected every 2-3 weeks for a total of up to four injections. Concentration of medication is 50mg/ml. Medication will be administered using a 1cc syringe with a 30gauge needle.

- Any competent patient (male or female) from the age of 18 to 89 that presents with any periocular pathology that requires skin graft for reconstruction and consents to participate will be a candidate to be included in the study.
- To your knowledge 5-FU hasn't been withdrawn from research or market in any country for any reason related to its safety or effectiveness.

2. STUDY OBJECTIVES

2.1 Primary Objective

- Determine the effectiveness of 5-FU on the change in measured graft size.

2.2 Secondary Objective(s)

- Patient and surgeon satisfaction using the scar assessment scale (POSAS) developed and previously published by Draaijers et al.
- Treatment related adverse events. Examples are pain, skin thinning, color/texture change, atrophy, telangiectasis, infection and erythema.
- Early post-operative complications (within 2 weeks of surgery). Example of that are wound dehiscence, graft necrosis, infection, bleeding, partial/complete graft failure and/or ectropion.

3. STUDY DESIGN

3.1 Study Design Description

- Randomized double blinded study comparing 5-FU versus placebo.
 - Patients will be randomized between treatment and control group. Double-masked study, neither patient nor physician providing treatment will know which group they are participating. Pharmacy will provide medication (5-FU versus saline).
 - Subject will be evaluated on first visit for the periocular pathology referred to our clinic requiring a full thickness skin graft to reconstruct the affected area. On that same visit patient will be scheduled to have surgery and research study will be presented. Whether or not patients decide to participate on study, surgery will be performed as normal. Then patient will be seen one week post-op as all surgical patients are normally seen. If patients decide to participate, 1-2 weeks later will start injecting medication (5-FU versus saline) on affected area. Injections will be repeated three more times, for a total of up to four, in a period of 2-3 weeks between each injection. After last injection is placed, patient will be seen 2-3 weeks after, and then 6 and 12 months after original surgery date. During each visit after surgery patient will be required to fill a scar assessment questionnaire.

3.2 Allocation to Treatment

- Patients will be randomly allocated between the two arms: treatment or control group by the MEEI Pharmacy Department.

3.2.1 Randomization Procedures

- Randomization will be performed by the research pharmacy per their protocol. The study will be conducted in a double-blind manner.

3.2.2 Masking Procedures

- Pharmacy will provide medication on the same syringe, no matter the group, with only patient's information.

3.2.3 Breaking the Mask (only if proposed study is *masked*)

- If any of the study participants suffer a serious adverse event, the identity of the study drug received by the subject will be given by the pharmacy for effective emergency treatment of the event.

4. SUBJECT SELECTION

4.1 Subject Inclusion Criteria

- Competent patient (male or female)
- Between ages of 18 and 89

Present with any ocular pathology requiring a full thickness skin graft

4.2 Subject Exclusion Criteria

- Women lactating, pregnant or planning to get pregnant
- Minors (<18 years old) or patients over 89 years old
- Immunosuppressed or immunocompromised
- Serious and active infection
- Dihydropyrimidine dehydrogenase enzyme deficiency
- Severe hepatic or renal failure
- Patient unable to consent

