5.5 Other Medications

- **Administration**

No limitation in concomitant medication use prior or during the clinical study participation.

- **Rescue Medication or Therapy**

No identifiable rescue medication or therapy that can be used during the participation in the clinical study.

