7.3 Study Drug or Device Procedures

- Every patient that participates on the study will obtain a physical examination with emphasis on the affected area in every visit. Plus patient will be required to fill out a scar assessment questionnaire. Also a photograph will be taken to monitor changes objectively.

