8. SAFETY AND EFFECTIVENESS ASSESSMENTS

8.1 Safety Assessments

- Patients will be asked in each visit after surgery for any adverse events or complain from surgery or injection. It will be documented in the record as normally done with any patient.
- The PI will be responsible for safety review. Physician may withhold any injection if there is an adverse event like infection

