9. ADVERSE EVENT RECORDING AND REPORTING

9.1 Recording Requirements

- Research subjects will be routinely questioned about treatment related adverse events at each study visit. All possible, if any, non-serious examples are pain, erythema/redness, skin thinning/atrophy, infection, color/texture change, swelling, telangiectasia, graft shrinkage/rejection and need for additional surgery. Serious adverse events are not expected to be seen at any moment of the study since medication has been shown to be safe to the patient. In addition, patients will be evaluated for early post-operative complications (within 2 weeks of surgery) not related to study drug treatment. Example of that are wound dehiscence, graft necrosis, infection, bleeding, partial/complete graft failure and/or ectropion. Events will be followed until it resolves or stabilizes; if needed other treatment (eg. antibiotics) will be added to manage adverse event.

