12. DATA HANDLING, RECORD-KEEPING AND MONITORING

12.1 Data Recording, Record-Keeping and Monitoring

- A Case Report Form (CRF) will be completed for each subject enrolled into the clinical study. The Sponsor-Investigator will review, approve and sign/date each completed CRF; the Sponsor-Investigator's signature serving as attestation of the Sponsor-Investigator's responsibility for ensuring that all clinical data entered on the CRF are complete, accurate and authentic. The physician will review the informed consent, confirm subject eligibility and verify the accuracy of data transfer from the source document to CRF. Data monitoring will occur monthly if new patients have been recruited during that specific time. Data review will be done by PI and study coordinator.
- Source Data are the clinical findings and observations, and test data/measurements, and other information contained in Source Documents. Source Documents are the original records (and certified copies of original records); including, but not limited to, hospital medical records, physician or office charts, physician or nursing notes, pharmacy dispensing records, recorded data from automated instruments, x-rays, etc. When applicable, information recorded on the CRF shall match the Source Data recorded on the Source Documents.
- The electronic data recording data system being used for this clinical research study has not been fully certified as being compliant with the FDA regulations at 21 CFR Part 11 due to the limited scope of this clinical research study.

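### Pregnancy is an entry exclusion, but no scheduled step requires asking about a new or newly planned pregnancy before each injection, and no stated stopping ground names it

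*Protocol*

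**What the plan says.** **Entry.** Protocol 4.2 excludes "Women lactating, pregnant or planning to get pregnant" and, in the same list, patients with suppressed immunity. Section 7.1 applies the criteria when the trial is offered. Section 12.1 adds, without a date, "The physician will review the informed consent, confirm subject eligibility and verify the accuracy of data transfer". Section 3.1 continues after the one-week visit with "If patients decide to participate, 1-2 weeks later will start injecting medication (5-FU versus saline) on affected area", so the decision to take part, and possibly the eligibility check, can be read as falling after surgery.

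**Dosing.** Sections 1.2, 5.1 and 7.8 put the first injection 2–3 weeks after surgery, followed by up to three more at intervals of 2–3 weeks. The concentration is 50 mg/ml and the maximum is 1 cc. Fifteen patients are planned for 5-FU.

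**Injection visits.** The table in 7.8 has four columns: injection, examination, questionnaire and photograph. Section 7.3 says "Every patient that participates on the study will obtain a physical examination with emphasis on the affected area in every visit"; the questionnaire is a scar assessment. Section 8.1 says "Patients will be asked in each visit after surgery for any adverse events or complain from surgery or injection", and 9.1 says "Research subjects will be routinely questioned about treatment related adverse events at each study visit".

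**Stopping.** Section 5.2 withdraws patients for non-compliance. Section 9.3 withdraws them for a serious event from the intervention and allows voluntary withdrawal after a minor one. Sections 7.7 and 8.1 let the physician withhold an injection for an adverse event, with infection as the example. Section 13.1 refers back to 5.2 and 9.3 and leaves the decision to the PI. Section 13.2 concerns stopping the whole study.

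**The concern.** Section 1.1 describes 5-FU as "irreversibly inhibiting the enzyme thymidylate synthetase resulting in impaired DNA synthesis". The protocol treats pregnancy as disqualifying at entry, at the dose it uses. The same reason applies at the fourth injection, up to 12 weeks after surgery. A site could complete every scheduled item and still inject 5-FU into a participant who has become pregnant, because no item requires the question. If the pregnancy is known and there is no adverse event, no written rule tells the physician to stop. What is at stake is the safety of a participant and a pregnancy.

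**Working it through.** The plan gives no figure for this point, and the sample-size calculation in SAP 10.3 does not bear on it. The check is the timing of the injections, a count, and a comparison of sections.

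**1. Timing** (1.2, 7.8). Injection k falls between 2 + 2(k − 1) and 3 + 3(k − 1) weeks after surgery. If eligibility is confirmed at injection 1, the status is 2(k − 1) to 3(k − 1) weeks old at injection k.

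| Injection | Weeks after surgery | Age of status (weeks) if confirmed at injection 1 |
|---|---|---|
| 1 | 2–3 | 0 |
| 2 | 4–6 | 2–3 |
| 3 | 6–9 | 4–6 |
| 4 | 8–12 | 6–9 |

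If eligibility is confirmed only before surgery, the age of the status is the middle column plus the wait for surgery.

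**2. Planned 5-FU injections with no scheduled question** (15 patients, 5.1).
- Confirmed at injection 1: 15 × 3 = 45.
- Confirmed only before surgery: 15 × 4 = 60.

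Both figures are before replacements, which 5.2, 13.1 and SAP 10.4 allow and which could add to them. Both include men and women past childbearing, since 4.1 admits ages 18 to 89.

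**3. Dose** (5.1). 1 ml × 50 mg/ml = 50 mg at most at any one injection, given locally.

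**4. Does a scheduled item require the question?**
- 7.8: none of the four columns does.
- 7.3: the examination emphasises the graft area and the questionnaire rates the scar.
- 8.1 and 9.1: the questions concern adverse events and complaints. A pregnancy without symptoms need not come up.
- 12.1: the eligibility check has no date. Even if placed at the first injection, nothing repeats it for injections 2 to 4.

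**5. Does a stopping ground name it?** Sections 5.2, 7.7, 8.1 and 9.3 rest on non-compliance or adverse events. Section 13.1 adds the PI's decision but no criterion for a newly met exclusion.

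**The case against.** Several replies have force.

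- *The change could still come to light.* A physician gives every injection, an examination is scheduled at each of these visits, 7.3 speaks of emphasis rather than restriction, and 13.1 gives the PI the decision. This stands. A reader might infer that nothing would reveal a pregnancy, or that the protocol obliges the physician to go on dosing. The documents support neither. They support only that nothing scheduled requires asking.
- *Entry screening already lowers the risk.* Women planning pregnancy are excluded, so what remains is an unplanned pregnancy or a changed plan within about 12 weeks of surgery. This stands and limits the size of the point, but it does not supply a later question.
- *New immunosuppression might seem an equal gap*, since 5.5 says "No limitation in concomitant medication use prior or during the clinical study participation". The support is thinner. The 8.1 question can be read as covering any adverse event, so the illness behind a new immunosuppressant may surface, and infection is only an example of a reason to withhold. The mechanism in 1.1 is a reason for concern in pregnancy; the documents give no reason why a small local dose would harm a newly immunosuppressed patient. It therefore belongs on the same question line, but with PI judgement and not an automatic stop.
- *The text is incomplete.* The consent pages and the opening page of each document were removed, and the protocol passes from section 5 to section 7. Instructions on pregnancy may stand in the removed pages.

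**Conclusion.** The point holds for the text available: pregnancy is an entry exclusion, no scheduled step requires asking about it again before each injection, and no stated stopping ground names it. The gap covers injections 2 to 4 if eligibility is confirmed at the first injection, and all four if it is confirmed only before surgery.

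The 45 to 60 injections might be taken as the number at risk. They are not: they count every planned 5-FU injection. The documents do not say how many participants could become pregnant, so neither an at-risk number nor an event rate can be given. The event may well be rare in an arm of 15. The case for acting is that the possible harm is serious and prevention costs little. The conclusion assumes that the removed pages contain no such check.

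**What to change.** 1. **Sections 7.3 and 7.8.** Before each of the four injections, ask whether the participant is or may be pregnant, or now plans pregnancy. On the same line, ask whether any other 4.2 condition, such as immunosuppression, is new.
2. **Section 13.1.** State that a participant who is pregnant or plans pregnancy receives no further injections, regardless of arm. Any other newly met 4.2 exclusion leads to withholding, and the PI decides on further dosing.
3. **Follow-up and mask.** In the same place, state that these participants stay in follow-up to 12 months and remain masked unless their care requires the assignment. Section 3.2.3 now names only a serious adverse event as a reason for release, so it needs a matching reference.
4. **Analysis.** State that they are kept in the ITT analysis. Without this, SAP 10.4 would drop and replace them as partly treated, and 13.1 would end their data collection at withdrawal.

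The cost is one CRF line at four existing visits and a few sentences of text, with no new visit or procedure. There are two downsides. A few participants would receive fewer injections, which slightly dilutes the treatment contrast once they are analysed as randomised. A question will also not detect a pregnancy that the participant has not recognised.

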5. STUDY DRUG(S)/DEVICE(S)

5.1 Study Drug Information

- Study drug that will be administered to fifteen of our patients is 5-Fluorouracil, FDA-approved systemic chemotherapy medication to treat certain cancers, the concentration 50 mg/ml and will inject less than 1cc total in the subcutaneous tissue of the affected area.
- Study placebo that will be administered to the other fifteen of our patients is sodium chloride 0.9% (PF).
- Medications will be given every 2 to 3 weeks for a total of 4 injections.
- The amount of medication injected will depend on the extension/dimension of the periocular area affected with a maximum dose of 1cc total.

5.2 Study Drug Compliance/Adherence

- Drug will be injected in office by the physician. Medication will be administered every 2 to 3 weeks.
- Patient will be withdrawn from study if patient doesn't follow post-operative instructions or is non-compliant with follow up appointments.
 - If a subject is withdrawn from study participation due to noncompliance/adherence will be replaced for another patient and will receive the corresponding medication.

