9.3 Withdrawal of Subjects due to Adverse Events

- If subject presents with a serious event from intervention, he/she will be withdrawn from further study intervention and the investigators will evaluate the reason for event. If patient states a minor adverse event patient will continue unless patient wishes to voluntary withdraw.
- A serious event includes a severe allergic reaction to medication causing systemic symptoms of anaphylaxis.
- Data will continue to be collected from the withdrawn subjects, until 12 months after original surgery date, but without further intervention (no more injections) and patient will not be included in the analysis.

Withdrawn subjects from study participation due to an adverse event will not be replaced for a new patient.

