13. STUDY DISCONTINUATION CRITERIA

13.1 Discontinuation of Individual Research Subjects

- Discontinuation criteria for individual research subjects has been previously addressed under section 5.2 (Withdrawal of subjects due to non-compliance/adherence) and section 9.3 (Withdrawal of subjects due to adverse events) of the clinical protocol. Decision will be done by PI. Data will be collected until subjects are withdrawn. If subjects have already received part of the treatment or withdrawn before treatment has been started then subjects will be replaced using the same eligibility criteria.

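### Protocol 5.2 appears to give a replacement patient the withdrawn patient's arm instead of a new random assignment, and SAP 10.4 drops the withdrawn patient from the analysis

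*Protocol*

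**What the plan says.** - Protocol 3.2: "Patients will be randomly allocated between the two arms". Protocol 3.2.1: "Randomization will be performed by the research pharmacy per their protocol". Neither section gives a ratio, a block scheme or an exception for replacements.
- Protocol 5.1 plans fifteen patients on 5-FU and fifteen on saline.
- Protocol 5.2: a subject withdrawn for not following instructions or missing visits "will be replaced for another patient and will receive the corresponding medication".
- Protocol 9.3: "Withdrawn subjects from study participation due to an adverse event will not be replaced for a new patient". Their data are still collected to 12 months, but they are left out of the analysis.
- Protocol 13.1 refers back to 5.2 and 9.3 and leaves the decision to the principal investigator. For subjects withdrawn before treatment or after part of it, it says: "then subjects will be replaced using the same eligibility criteria". It is silent on the replacement's arm, and it collects data only up to withdrawal.
- SAP 10.4 announces an intention-to-treat comparison of all randomised subjects. It then excludes and replaces anyone who is partly treated, leaves early or is lost to follow-up, again without saying how the replacement is allocated.
- SAP 10.3 plans up to 15 per arm, allows for 20% dropout, and permits the analysis once 10 per arm have completed.

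**The concern.** Two things go wrong together.

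First, the replacement's arm is set by who withdrew and not by a new draw. If withdrawals are more frequent in one arm, later recruits are steered towards that arm, so treatment becomes associated with time of entry.

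Second, withdrawal happens after randomisation and may depend on treatment. Protocol 9.1 lists pain, redness and skin changes as possible treatment-related events, and these could affect attendance. Removing such patients and refilling their places in the same arm restores the planned 15/15 on paper. The analysed groups are then no longer the randomised groups, and the imbalance in withdrawals no longer shows in the arm sizes. The t-test on mean change in graft size would compare patients selected partly on tolerance and attendance.

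A secondary risk is predictability. The principal investigator decides on withdrawal (13.1) and reviews the study monthly for adverse or treatment effects (11.1). Anyone who had formed a view of a withdrawn patient's arm could predict the arm of the next patient enrolled in that place.

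**Working it through.** **1. The plan's sample size.** Inputs from SAP 10.3: difference 13.2%, SD 10%, two-sided alpha 0.05, power 80%, equal-variance t-test.

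- Normal approximation: n per arm = 2 × (1.960 + 0.842)² × 10² / 13.2² = 2 × 7.851 × 100 / 174.24 = 9.01, rounded up to 10.
- Exact (noncentral t) power at 10 per arm is 0.797, so the stated total of 20 at 80% power reproduces.
- Dropout: 10 × 1.2 = 12 per arm, as stated. Dividing instead, 10 / 0.8 = 12.5, gives 13. The planned 15 per arm exceeds both.

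**2. Places filled by replacement.** Assume each patient first entered withdraws with probability d and every withdrawal is replaced under the 5.2 rule. The expected number of analysed places held by a replacement is then d × N.

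| Assumed dropout d | Expected places of N = 30 |
|---|---|
| 10% | 3 |
| 20% (SAP 10.3) | 6 |
| 30% | 9 |
| 40% | 12 |

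At d = 20% the expected count is 4 of 20 and 4.8 of 24. With independent withdrawals, the binomial chance that more than 20% of places are replaced is 0.37 for N = 20, 0.54 for N = 24 and 0.39 for N = 30. So 20% is an expected share and not a maximum.

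The SAP's 20% is also not split by reason. Protocol 5.2 covers non-compliance only, and 9.3 does not replace adverse-event withdrawals. The share under 5.2 alone is therefore probably below these figures, and the documents give no rate for it.

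**3. Is arm-matched replacement needed for power?** Same inputs, exact t-test power:

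- No replacement, 15 per arm, 20% dropout: 15 × 0.8 = 12 per arm, power 0.871.
- The 10 completers per arm are met on average up to one-third dropout (15 × 2/3 = 10).
- 30 completers: 0.937 at 15/15, 0.936 at 16/14, 0.933 at 17/13, 0.928 at 18/12.

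**4. Imbalance if additional patients are randomised.** Assume simple randomisation (the documents do not state the method), 3 withdrawals per arm and 6 additional patients. Completers start at 12/12. If k of the 6 go to one arm, the arms differ by |2k − 6|, which is 4 or more when k = 0, 1, 5 or 6. The probability is (1 + 6 + 6 + 1) / 64 = 14/64 = 0.22. The extreme split is 18/12.

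**The case against.** The wording of 5.2 does not name the arm. It could mean whatever the pharmacy assigns under 3.2 and 3.2.1, which make no exception for replacements. That reading is possible but less natural, and the fixed fifteen and fifteen in 5.1 favours filling the vacated place in the same arm. If the sponsor did mean a new assignment, the sentence still has to say so.

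It is also fair to say that the inherited place was itself randomly generated, that the pharmacy holds the allocation, and that the syringes do not differ: "Pharmacy will provide medication on the same syringe, no matter the group, with only patient's information". Clinic staff would not normally know the withdrawn patient's arm. This stands, and it is why predictability is only a secondary risk. It does not answer the dependence on withdrawal, which operates with masking intact.

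A reader might infer a stronger point: that after a mask break the investigators would know the replacement's arm in advance. The documents do not support this. Under 3.2.3, "the identity of the study drug received by the subject will be given by the pharmacy" only after a serious adverse event, and 9.3 says adverse-event withdrawals are not replaced. The broader sentence in 13.1 conflicts with 9.3, but it mentions only eligibility. The same-medication wording appears only in 5.2, for non-compliance.

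Finally, the exclusion in SAP 10.4 would threaten the comparison even without 5.2. That is true, and it is why changing 5.2 alone is not enough.

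**Conclusion.** The point holds. On its natural reading, 5.2 places replacements without a new randomisation, contrary to 3.2 and 3.2.1. Combined with the exclusion in SAP 10.4, it lets a post-randomisation event decide part of the analysed sample, contrary to that section's own intention-to-treat statement.

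The size is about 6 of 30 places (20%), provided that the planned 20% dropout occurs and every dropout is replaced under this rule. A reader might take a fifth as the upper limit. It is not, because the 20% is an all-cause planning assumption and no section caps the number of replacements.

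The direction and size of any bias cannot be derived from the documents. If withdrawal were unrelated to arm and masking held, the bias could be negligible. The plan gives no ground for assuming this, and arm-matched replacement brings almost no gain in power to set against the risk.

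**What to change.** - **Protocol 5.2:** replace the clause on the replacement's medication with a statement that any additional patient takes the next unused assignment on the pharmacy's randomisation list.
- **SAP 10.4:** delete the exclude-and-replace rule. Analyse withdrawn patients in their assigned arm, using the data collected. State a simple rule for a missing final graft measurement.
- **Protocol 9.3 and 13.1:** align with this the exclusion from analysis in 9.3 and the end of data collection at withdrawal in 13.1. Reconcile the two sections on whether adverse-event withdrawals are replaced.

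The required number is unchanged at 10 completers per arm. Arms may end somewhat unequal: by 4 or more with probability about 22% for 6 additional patients under assumed simple randomisation. The power cost is small, 0.937 at 15/15 against 0.928 at 18/12. The change to 5.2 is wording only. Keeping withdrawn patients in the analysis asks more: continued measurement after withdrawal where the patient agrees, and the missing-data rule.
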